3.4 Interim Analysis

A pivotal analysis and interim report of the primary endpoint data is planned after 3-month follow-up data is collected for the BIO-CONDUCT study patients and the minimum sample size for primary endpoint 1 and primary endpoint 2 has been met. In addition to analyzing primary endpoints 1 and 2, the interim report will also summarize the additional data collected at time of analysis, including but not limited to Solia S LBBA lead measurements and non-Solia S adverse event rates. Poolability analysis for sites and regions, as well as analysis by sex and gender, will also be completed at time of interim analysis.

Further interim analyses are not planned and there are no statistical criteria to stop the study early. Thus, no adjustment of the significance level is planned due to the pivotal analysis.

3.5 Study Success

For the study to be considered successful, both primary endpoints must be met to control the type I error at the 1-sided 0.025 level. Secondary endpoint 1 will only be tested if both primary endpoints are successful.

4 Analysis Methods

4.1 Endpoint Analyses

4.1.1 Primary Endpoint 1 - Serious Adverse Device Effect (SADE)-Free Rate Through 3 Months Post-Implant

The purpose of primary endpoint 1 is to evaluate the serious lead related adverse device effects related to Solia S lead utilized or attempted to be implanted in the LBB area and

serious implant procedure events related to the Solia S LBB lead that occur through 3 months post-implant.

The following hypotheses have been defined to evaluate the primary endpoint "Serious adverse device effect (SADE)-free rate through 3 months post-implant":

H_0 : The serious adverse device effect (SADE)-free rate through 3 months post-implant is less than or equal to 87.5%

$$\text{SADE-free rate} \leq 87.5\%$$

H_a : The serious adverse device effect (SADE)-free rate through 3 months post-implant is greater than 87.5%

$$\text{SADE-free rate} > 87.5\%$$

Primary endpoint 1 will be evaluated by performing an exact, one-sided binomial proportion test comparing the observed proportion (overall SADE-free rate through 3 months) to the performance goal of 87.5%. The lower, two-sided 95% confidence bound for the overall SADE-free rate must be greater than 87.5% to reject the null hypothesis (H_0), which would demonstrate evidence that the SADE-free rate is significantly higher than 87.5%.

For the primary endpoint 1 analysis, ITT population subjects who have at least 76 days of follow-up (corresponding to the earliest potential in-window 3-month visit) or experienced the primary safety endpoint will be included. A Kaplan-Meier survival analysis (time-to-event) for the primary endpoint outcome will also be performed.

Subjects without a primary safety endpoint event with less than 76 days of follow-up will be excluded from the Kaplan-Meier survival analysis and the binomial proportion test to avoid overestimation of the SADE-free rate.

Sample Size Determination for Primary Endpoint 1

Prior studies evaluating the safety of Solia S when implanted in the right ventricle has demonstrated a high SADE-free rate, between 94.3% and 98.5% (Master Study of the Siello Pacemaker Lead and Siello IDE Clinical Study, data on file). When implanting in the LBB area, the expected safety needs to consider the change in implant location. A summary of published data that includes safety information for leads implanted in the LBB area is presented in Table 2.

Table 2: LBB Area Pacing—Published Safety Results

Study	Mean Follow-up Duration (months)	Total Implanted Subjects (n)	Subjects without SADE (n)	SADE-Free Rate	95% CI – Lower Bound
Su L et al. 2021	18.6	618	600	97.1%	95.4%
Vijayaraman P et al. 2019	5.2	93	87	93.6%	86.4%
De Pooter J et al. 2021	3.0	44	39	88.6%	75.6%
Li X et al. 2019	3.0	30	29	96.6%	81.9%

Based on this information, it is anticipated the Solia S lead will have a safety profile similar to published literature for leads implanted in the LBB area with an expected SADE-free rate of at least 93.0%. The assumed performance (93%) and performance goal of 87.5% are compared to the published safety results in Figure 1.

[figure not shown]

Figure 1: Assumed Safety Performance Compared to Published Results

The estimated sample size required to evaluate primary endpoint 1 is based on a superiority comparison of overall Solia S lead serious adverse device effect free-rate to 87.5% through 3 months post-implant. The sample size for primary endpoint 1 was calculated based on the following assumptions.

- Study Design: Non-randomized
- Type I error (alpha): 0.025 (one-sided for superiority)
- Statistical power: 80%
- Performance Goal for SADE-Free Rate through 3 months post-implant: 87.5%
- Expected SADE-Free Rate through 3 months post-implant: 93% (Based on Literature Review/Master Study)
- Test basis: Exact binomial test
- Attrition Rate: 5%

For primary safety endpoint 1, a total of 247 evaluable Solia S leads would be required to demonstrate superiority to a SADE-free rate of 87.5%. Assuming a 5% attrition rate, a total of 260 (= 247 / 0.95) patients with a Solia S lead would be required to be enrolled to evaluate Primary Safety Endpoint 1.

Justification of Pooling for Primary Endpoint 1

Justification of pooling data from other prospectively collected data sources will include the following considerations:

- Design of study including but not limited to inclusion/exclusion criteria, follow-up visit schedule, and required procedures/data collection
- Implanted devices included in the study
- Criteria for success of Solia S LBB area implants
- Study organization and level of monitoring
- Availability of subject level data and, when required, documentation supporting reported adverse events

Data from studies that are determined to be similar to BIO-CONDUCT with regards to the considerations above may be pooled for analysis of primary endpoint 1. A poolability analysis will be conducted to examine heterogeneity (Section 4.4).

Specifically, it is planned that for evaluation of primary safety endpoint 1, data from subjects in the BIO|MASTER.Selectra 3D study (NCT04323670) with a successful Solia S lead LBB area implant will be pooled with data from the BIO-CONDUCT study. The BIO|MASTER.Selectra 3D study was a multi-center, prospective, non-randomized post-market study designed to evaluate the clinical safety, performance, and handling of the Selectra 3D catheter when used for conduction system pacing implants (His bundle or LBB area) of the Solia S lead. Additionally, performance and safety of the Solia S lead was collected. A total of 157 subjects were enrolled into the BIO|MASTER.Selectra 3D study from October 8, 2020 to November 18, 2021 across 10 study sites in Europe, Asia, and Australia.

Only subjects enrolled into the BIO|MASTER.Selectra 3D study with a successful Solia S lead LBB area implant and at least 76 days of follow-up or with a Solia S lead LBB area implant attempt and qualifying primary safety endpoint event will be included in pooled analysis with the BIO-CONDUCT ITT population. All potential endpoint events occurring in the BIO|MASTER.Selectra 3D study (i.e., serious Solia S LBB lead events and serious procedure related events) will be adjudicated by the BIO-CONDUCT CEC and adjudication outcomes will be utilized for the analysis of primary endpoint 1.

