related to the Solia S LBB lead that occur through 3 months post-implant, where a Solia S LBB lead includes leads that were implanted or attempted to be implanted in the LBB area. The period of observation starts from the time of the first attempt to implant the Solia S lead in the LBB area through 3 months (90 days) post-implant. Additionally, if an AE meeting primary endpoint 1 criteria is reported after the date of the 3-month follow-up, but on or before 3 months post-implant, this AE will be included in the primary endpoint 1 analysis.

The AE classification, category, resolution and relation to the study device (Solia S LBB lead) for each individual event will be determined by the Clinical Event Committee (CEC) (see Section 9.3).

All SADEs for which the CEC determines the event is causally related or probably related to the Solia S LBB lead will be included in the primary endpoint 1 analysis. In addition, the following serious procedure related events will also be included:

- Pneumothorax directly associated with the Solia S LBB lead or Solia S LLB lead implant procedures
- Cardiac perforation with or without tamponade caused by the Solia S LBB lead or Solia S LLB lead implant procedures

Adverse events with a final CEC adjudicated relation of not related or possible relation will not contribute to or be included in the evaluation of primary endpoint 1.

Finally, subject deaths resulting from a Solia S LBB lead AE will be included in the primary endpoint analysis.

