4.1.4 Secondary Endpoint 2: SADE-Free rate through 6 Months and 12 Months Post-Implant

There are no formal hypotheses for secondary endpoint 2. The SADE-free rate at each timepoint will be calculated as the number of subjects without one or more Solia S LBB lead adverse event divided by the total number of study subjects successfully enrolled and subjects undergoing an unsuccessful implant attempt who have a qualifying Solia S LBB lead complication in percent. A Kaplan-Meier survival analysis (time-to-event) for the will also be performed for each timepoint.

For the secondary endpoint 2 analysis at 6 months, ITT population subjects who have sufficient follow-up data (at least 152 days of follow-up, corresponding to the earliest potential in-window 6-month visit) or experienced a Solia S LBB lead adverse event will be included. Subjects without a Solia S LBB lead adverse event who drop out prior to day 152 will be excluded from the analysis.

For the secondary endpoint 2 analysis at 12 months, ITT population subjects who have sufficient follow-up data (at least 335 days of follow-up, corresponding to the earliest potential in-window 12-month visit) or experienced a Solia S LBB lead adverse event will be included. Subjects without a Solia S LBB lead adverse event who drop out prior to day 335 will be excluded from the analysis.

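### The Kaplan-Meier analysis of the SADE-free rate deletes event-free early dropouts instead of censoring them, and SAP 4.1.4 extends the rule and misstates the event

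*SAP*

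**What the plan says.** SAP 4.1.1 tests primary endpoint 1 with an exact binomial test against 87.5% and adds a Kaplan-Meier analysis. Subjects enter if they have at least 76 days of follow-up or had a primary safety event at any time. For the rest, "Subjects without a primary safety endpoint event with less than 76 days of follow-up will be excluded from the Kaplan-Meier survival analysis", and also from the binomial test, "to avoid overestimation of the SADE-free rate". The Protocol's definition of primary endpoint 1 observes events "through 3 months (90 days) post-implant".

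The pooling paragraphs of SAP 4.1.1 apply the same entry rule to BIO|MASTER.Selectra 3D subjects, who need a successful implant and "at least 76 days of follow-up or with a Solia S lead LBB area implant attempt and qualifying primary safety endpoint event".

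SAP 4.1.4 (secondary endpoint 2) says: "A Kaplan-Meier survival analysis (time-to-event) for the will also be performed for each timepoint". The noun naming the outcome is missing. It then sets cut-offs at day 152 for 6 months and day 335 for 12 months; for the latter, "Subjects without a Solia S LBB lead adverse event who drop out prior to day 335 will be excluded from the analysis". On the event, "The SADE-free rate at each timepoint will be calculated as the number of subjects without one or more Solia S LBB lead adverse event", while the denominator adds failed attempts through "an unsuccessful implant attempt who have a qualifying Solia S LBB lead complication". SAP 2.2.2 and the title of 4.1.4 call the endpoint a SADE-free rate, and Table 1 in SAP 3.2 ties its population to a qualifying primary safety endpoint event.

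**The concern.** The stated reason belongs to one of the two analyses it is applied to. In a simple proportion, a subject lost at day 20 without an event must be either left out or counted as a success, and counting as a success overstates the rate. Kaplan-Meier has a third option: the subject stays in the risk set until day 20 and is then censored, with no credit for time not observed.

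Under the SAP rule, a subject with short follow-up is kept if an event occurred and deleted if not. That removes event-free person-time from the risk sets and leaves every event in place, so the curve is too low if dropout is independent of event risk. With no censoring left before day 76, the curve also equals the simple proportion up to that day. It still shows when events occur, but as an estimate of the rate it hardly differs from the binomial result and gives no check on early dropout. Dropout accumulates towards 12 months, so the effect grows there.

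The event wording in 4.1.4 is a second problem in the same analysis. Read literally, the 6- and 12-month rates would count non-serious lead events and could not be set beside the 3-month rate.

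**Working it through.** **The plan's own figure.** Inputs from SAP 4.1.1: goal 87.5%, expected rate 93%, one-sided alpha 0.025, power 80%, attrition 5%. The normal-approximation formula gives

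[(1.960·√(0.875·0.125) + 0.842·√(0.93·0.07)) / 0.055]² ≈ 246.2, rounded up to 247, and 247/0.95 = 260.

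Both agree with the SAP.

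**Worked case.** 260 subjects, 13 event-free subjects lost before day 76 (5%), 18 events at implant (260 × 0.07 = 18.2).

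- Censoring: 1 − 18/260 = 93.08%.
- SAP exclusion: 1 − 18/247 = 92.71%, which is 0.36 points lower.

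**General formula.** Let p be the event risk by the end of the window, d the probability of dropout before the cut-off day (independent of events), and m the event probability accrued by the time of dropout, averaged over dropout times.

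- Share of subjects kept: 1 − d(1 − m)
- Share with an observed event: p − d(p − m)
- Kaplan-Meier with the exclusion (no censoring after the cut-off): 1 − [p − d(p − m)] / [1 − d(1 − m)]
- Kaplan-Meier with censoring: 1 − p on average
- Proportion counting dropouts as successes: 1 − [p − d(p − m)]

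**3 months.** p = 0.07 and d = 0.05 from the SAP. Assumed: dropout uniform over days 0 to 76; a fraction of events at implant and the rest uniform over 90 days.

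| Early events | m | Kept | Observed events | With exclusion | Shortfall | Dropouts as successes |
|---|---|---|---|---|---|---|
| 0% | 0.0296 | 0.9515 | 0.0680 | 92.86% | 0.14 | 93.20% |
| 50% | 0.0498 | 0.9525 | 0.0690 | 92.76% | 0.24 | 93.10% |
| 90% | 0.0660 | 0.9533 | 0.0698 | 92.68% | 0.32 | 93.02% |

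The limits follow from the formula. If all dropouts precede the events (m = 0), the result is 93.0% and the shortfall is 0. If all events precede the dropouts (m = p), it is 1 − 0.07/0.9535 = 92.66%, a shortfall of 0.34. These are averages; a single data set can differ slightly, as the worked case does.

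A simulation with 260 subjects and 10,000 runs, placing the early events in the first two days, agrees: 92.86, 92.77 and 92.67% with exclusion, against 93.00, 93.01 and 92.99% with censoring. The last column of the table confirms that the overestimation argument is right for the proportion.

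**Days 76 to 90.** The curve and the proportion can part only if an event follows a censoring in this interval. With 1 to 2% censoring there, the simulated mean difference was 0.01 points or less.

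**6 and 12 months.** The documents give no risk or attrition for these times, so all inputs are assumptions. The same formula is used with windows of 180 and 365 days, cut-offs at 152 and 335 days, and 0 to 90% early events.

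| Time | Risk p | Loss d | Shortfall (points) |
|---|---|---|---|
| 6 months | 8% | 5% | 0.16 to 0.36 |
| 6 months | 8% | 15% | 0.54 to 1.21 |
| 12 months | 7 to 9% | 5% | 0.16 to 0.41 |
| 12 months | 7 to 9% | 10% | 0.33 to 0.85 |
| 12 months | 7 to 9% | 20% | 0.74 to 1.90 |

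**Event wording.** No arithmetic applies. Three terms stand for one event: lead adverse event (numerator and exclusion rules of 4.1.4), complication (denominator of 4.1.4) and qualifying primary safety endpoint event (Table 1). Only the last carries the seriousness and adjudication requirements of the primary endpoint.

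**The case against.** The strongest reply is that nothing turns on this. Kaplan-Meier carries no decision rule, the exclusion is explicit and prespecified, and it gives both analyses the same subjects. The 3-month shortfall is small beside the exact 95% interval at 229/247, about 88.7% to 95.6%. All of this stands and is why the point is minor.

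Second, censoring assumes that dropout is unrelated to event risk. If early dropouts are at higher risk, a censored curve overstates the SADE-free rate, and a lower curve may lie nearer the truth. This is a fair limit on censoring, but deletion does not correct informative dropout; it only moves the estimate down by an amount unrelated to the dropouts' risk. The missing-data sensitivity analyses in SAP 3.3 are optional and confined to the primary endpoints.

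Third, the 4.1.4 exclusions refer only to the analysis and do not name Kaplan-Meier. This is correct. Applying them to Kaplan-Meier is the natural reading given 4.1.1 and the lack of any exemption, but it is a reading.

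Fourth, the title of 4.1.4, SAP 2.2.2 and the reliance on adjudicated events in SAP 3.1 show that SADEs are probably meant, and SAP 2.2.1 itself uses complication loosely for primary endpoint 1. The intent is indeed fairly clear; the formula a programmer would follow is not.

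**Conclusion.** The concern holds and is minor. The 4.1.1 rule makes the Kaplan-Meier estimate too low under independent censoring: 0.14 to 0.32 points on average at 3 months with the SAP's 93% rate and 5% attrition, and between 0 and 0.34 across all timings of events and dropout. The later figures depend on assumed risk and loss: 0.2 to 1.2 points at 6 months, and at 12 months 0.2 to 0.4 at 5% loss or 0.3 to 1.9 at 10 to 20% loss. The upper end needs heavy loss and mostly early events and is illustrative only. The bias is against the device, and correcting the curve leaves the primary test, its power and study success unchanged. The event wording in 4.1.4 is inconsistent with the endpoint it implements and should be corrected whatever is decided on censoring.

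**What to change.** In SAP 4.1.1 and 4.1.4, include every subject of the analysis population in Kaplan-Meier and censor event-free subjects at last follow-up. Report the day-90, 6-month and 12-month estimates with 95% confidence intervals. Keep the 76-, 152- and 335-day rules, and the overestimation rationale, for the proportions only.

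Apply the same to BIO|MASTER.Selectra 3D subjects with a successful implant and under 76 days of follow-up. This means limiting the pooled entry rule in 4.1.1 to the proportion. The documents do not say whether any such subjects exist.

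In 4.1.4, supply the missing noun and replace both event terms with the primary endpoint 1 definition (the same adjudicated event types), with the window extended to 6 and 12 months.

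The cost is an SAP amendment. No new assessments are needed, and Table 1 and the primary test stay as they are. Table 1 still admits failed attempts only when they had an event; this change does not address that. The price of censoring is reliance on independent dropout, which the report should state.

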2.1 Study Objectives

2.2 Study Design

BIO-CONDUCT is a prospective, non-randomized, multi-center, investigational device exemption (IDE) study. This clinical investigation is designed to enroll up to 260 subjects who will be followed for at least 12 months post-implant at up to 25 clinical study sites within the United States (U.S.). The design allows for pooling of data with other prospectively collected data sources to supplement the LBB area pacing population to achieve the sample size of 260 subjects with 3 months of follow-up needed for primary safety endpoint 1 analysis. Thus, the number of prospectively enrolled subjects in the BIO-CONDUCT study may be less than 260. At least 50% of the subjects included in the analysis will be from the BIO-CONDUCT study.

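### Under the exact binomial test that the SAP names, 247 evaluable subjects give 79.2% power for primary endpoint 1, slightly below the stated 80%; the figure matches a normal approximation

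*SAP*

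**What the plan says.** SAP 4.1.1 prescribes the analysis as "performing an exact, one-sided binomial proportion test comparing the observed proportion (overall SADE-free rate through 3 months) to the performance goal of 87.5"%. The null hypothesis is rejected if the lower limit of the two-sided 95% confidence interval lies above that goal.

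For the sample size, the same section works with a one-sided alpha of 0.025, a target power of 80%, a goal of 87.5%, an anticipated rate of 93% and attrition of 5%. The method appears in that list as "Test basis: Exact binomial test".

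From these the SAP concludes that "a total of 247 evaluable Solia S leads would be required to demonstrate superiority to a SADE-free rate of 87.5"%, and it inflates 247 to 260 enrolled. SAP 2.2 describes the target a little differently, allowing pooling with other data "to achieve the sample size of 260 subjects with 3 months of follow-up needed for primary safety endpoint 1 analysis". So the SAP attaches two counts to this endpoint, 247 evaluable and 260. It names no formula or software for the calculation.

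**The concern.** The stated basis and the stated size do not agree. A reader who takes the five inputs and runs the exact test does not get 80% at 247, and no usual exact criterion returns 247 as the answer. A statistical reviewer is likely to repeat this calculation. The endpoint is one of two that must both be met for study success (SAP 3.5), and the pivotal analysis is meant to support a PMA submission (SAP 3).

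What is at stake is the accuracy of a stated power and of its stated basis. The validity of the test is not in question.

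**Working it through.** **Inputs** (all SAP 4.1.1): p0 = 0.875, p1 = 0.93, one-sided alpha 0.025, target power 80%, single arm.

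**1. Reproducing 247.** The one-sample normal formula is

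n = [(z₀.₉₇₅·√(p0(1−p0)) + z₀.₈₀·√(p1(1−p1))) / (p1−p0)]²

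= [(1.960 × 0.3307 + 0.8416 × 0.2551) / 0.055]² = 246.17, which rounds up to 247.

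Attrition: 247/0.95 = 260. Both SAP figures reproduce.

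Other approximations do not give 247: arcsine 224, null variance only 284, alternative variance only 169, and continuity-corrected 256 or 265.

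**2. The same formula for primary endpoint 2** (80% versus 88%, SAP 4.1.2, also labelled exact):

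[(1.960 × 0.4 + 0.8416 × 0.3250) / 0.08]² = 174.73, which rounds up to the SAP's 175. Exact power at 175 is 79.5% (at most 24 failures).

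**3. The exact test.** For each n, take the smallest r with P(X ≥ r | n, 0.875) ≤ 0.025. Power is P(X ≥ r | n, 0.93), and n − r is the largest number of failures that still rejects H0.

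| n evaluable | Max. failures | Actual alpha | Power at 93% |
|---|---|---|---|
| 245 | 20 | 2.08% | 80.2% |
| **247** | **20** | **1.86%** | **79.2%** |
| 251 | 20 | 1.49% | 77.1% |
| 252 | 21 | 2.39% | 83.1% |
| 258 | 21 | 1.74% | 80.3% |
| **260** | **21** | **1.56%** | **79.3%** |
| 261 | 22 | 2.46% | 84.8% |

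Allowing a 21st failure at 247 would give an alpha of 3.08%, so 20 is the limit there.

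**4. Shape of the power curve.** Exact power first reaches 80% at n = 232 (80.3%). Near the planned size it is at or above 80% for 242–245 and 252–258, and below 80% for 246–251 and 259–260. It stays at or above 80% from 261 (checked to 499). Neither the first crossing (232) nor the sustained one (261) is 247.

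**5. Size of the shortfall.** 80 − 79.2 = 0.8 points at 247, and 80 − 79.3 = 0.7 points at 260.

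**The case against.** The case for leaving this alone has real weight.

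- A gap of 0.7 to 0.8 points is within ordinary planning tolerance. This stands, and it is why the point is minor.
- The gap is small beside the uncertainty in the assumed rate. The SAP expects at least 93.0%. At a true rate of 93.05%, exact power at 247 is already 80.1%, and at 93.5% it is 87.3%. This stands too.
- The analysis itself is exact, so type I error is controlled and the decision rule is unambiguous whatever n occurs. This stands.
- The exact label might describe only the analysis test. It is possible, but the label sits in the list of sample-size assumptions, where a reader will take it as the basis for 247. It also remains an inference that 247 came from a normal approximation. Two matches to the unit make that likely but do not prove it. The shortfall does not depend on it.

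A reader might go further and infer that the primary safety test really has about 77% power. The documents do not support that. The figure 77.1% belongs to n = 251, which the SAP never sets. It is the bottom of a saw-tooth, and one more subject gives 83.1%. The evaluable count may land elsewhere between 247 and 260, because event-free subjects with under 76 days of follow-up are excluded and other data are pooled. Over that range, equally weighted, power averages 80.1%.

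A reader might also infer that a target of 252 evaluable fits safely within 260. If 5% attrition applies only to the BIO-CONDUCT part, 130 BIO-CONDUCT subjects leave 260 − 6.5 = 253.5, but 200 leave 260 − 10 = 250, which is in the trough. SAP 2.2 fixes only the 50% floor (130 of 260), and SAP 4.1.1 gives no count of LBB implants among the 157 BIO|MASTER.Selectra 3D subjects. The claim therefore rests on an assumed split.

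**Conclusion.** The point holds as a minor error in a stated power and its stated basis. Under the test that SAP 4.1.1 names, neither count attached to primary endpoint 1 reaches 80%: power is 79.2% at 247 and 79.3% at 260, for a true SADE-free rate of exactly 93% and a one-sided alpha of 0.025. The figure 247 agrees to the unit with a normal approximation and with no usual exact criterion.

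Type I error stays below 0.025 at every n, and the conclusion drawn from any given data set would be the same. The documents do not support reading this as an underpowered study or an invalid design.

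**What to change.** Make one of two wording changes in SAP 4.1.1:

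- state that exact power is 79.2% at 247 evaluable subjects, with H0 rejected if there are 20 or fewer failures; or
- keep 247 and describe it as based on a normal approximation, with the exact test used for the analysis.

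The same choice applies to the 175 in SAP 4.1.2, where exact power is 79.5%.

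Optionally, add a sentence saying that exact power varies with the evaluable count, from 77.1% (n = 251) to 83.1% (n = 252) between 247 and 260, and stays at or above 80% only from 261. If the sponsor wants 80% whatever count is reached, 261 evaluable is the threshold, which at 5% attrition means 261/0.95 = 274.7, or 275 enrolled. If the sponsor prefers a target of 252 within the existing 260, the SAP should say that this depends on an assumed split between BIO-CONDUCT and BIO|MASTER.Selectra 3D subjects.

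The wording change costs a short SAP amendment and a stated power slightly under 80%. It needs no extra subjects and no change to the test. Only the option of 261 evaluable adds enrollment, 275 − 260 = 15 subjects if 5% attrition applies throughout.
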